#### PFIZER CONFIDENTIAL

- 5. HIRD only: To evaluate possible impact of missing information on medical history, we will consider extending the baseline period to 18 months. To assess if there are important differences between the populations with at least 12 months and 18 months of continuous HIRD enrollment, the HR of endometrial cancer will be calculated for LDVE users versus non-users among women who have a baseline period of at least 18 months of continuous HIRD enrollment. Comparing results using different baseline durations will assess the effect of potential misclassification of covariates and the balance with increased random error due to decreased study size (Annex 1: Table 8).
- 6. HIRD and Sweden: To determine if associations between vaginal estrogen, non-users, and E+P HT and endometrial cancer differ according to a patient's history of cancer, a sensitivity analysis will be conducted. to estimate and compare the IRs of endometrial cancer among women by history of cancer other than endometrial cancer and basal cell carcinoma (if case counts are sufficient to support estimation) in the following groups (Annex 1: Tables 9 and 13):
  - a. LDVE new users versus non-users of vaginal estrogen.
  - b. MDVE new users versus non-users of vaginal estrogen.
  - c. HDVC new users versus non-users of vaginal estrogen (HIRD only).
  - d. LDVE new users versus E+P HT new users of hormone therapy.
  - e. MDVE new users versus E+P HT new users of hormone therapy.
  - f. HDVC new users versus E+P HT new users of hormone therapy (HIRD only).
- 7. HIRD only: To identify the rate of endometrial cancer in patients who may have a cumulative exposure that is higher than the intended average daily dose, the rate of endometrial cancer will be estimated among HDVC new users compared to non-users of vaginal estrogen and HDVC new users compared to E+P HT new users stratified by number of dispensings. Number of dispensings will be categorized as ≤ 2 dispensings per year and >2 dispensings per year(Annex 1: Table 10).
- 8. HIRD only: To evaluate possible effects of dose of vaginal estrogen on risk of endometrial cancer among vaginal estrogen new users (the full study population), the HR of endometrial cancer will be calculated for HDVC new users versus LDVE new users (Annex 1: Table 10).
- 9. HIRD and Sweden: A quantitative bias analysis will be conducted to evaluate the impact of potential under-ascertainment of hysterectomy and misclassification of prior use of systemic estrogens or other estrogen- or progestogen-containing products on effect estimates of endometrial cancer rate with LDVE use (Annex 1: Table 11 and Table 12). There may be women whose hysterectomy, prior estrogen use (including prior E+P HT use), or prior progestogen use is not captured in the data sources in each country prior to the index date, in which case, they would not have been excluded at baseline. This analysis will use plausible

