#### PFIZER CONFIDENTIAL

[figure not shown]
HIRD: A minimum of 12 months of continuous eligibility in the HIRD prior to and including the study drug dispensing date, or the gynecological visit date for non-users.

Sweden: A minimum of 24 months of medical history (i.e., 24 months of continuous residence in Sweden with no migration observed) prior to and including the study drug dispensing date, or the gynecological visit date for non-users.

The reason for using different baseline requirements is that greater turnover in the HIRD reduces the duration of enrollment, and one wishes to preserve available enrollment for follow-up. The baseline period includes all available enrollment data (HIRD) and medical history (HIRD, Sweden) on and prior to the index date (date of first dispensing of a study drug or gynecological visit).

4. Must be enrolled (HIRD) or residing in Sweden (Swedish registers) on the day after the index date.

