### 9.3.4. Baseline Covariates

The study will identify and describe baseline covariates and prior use of estrogen and progestogen use using all available data prior to and including the index date (see Section 9.1.1 Time Periods). A continuous variable measuring the duration of use will be created for each of the following drug categories:

- Single-entity progestogen contraceptives (oral, transdermal, or injectable);
- E+P contraceptives (oral, transdermal, or injectable).
- Unopposed estrogen hormone therapy: These include oral, transdermal, and injectable singleentity estrogen medications without a progestin dispensed during the baseline period.
- Unopposed progestin hormone therapy: These include oral, transdermal, injectable, and vaginal medications without an estrogen dispensing during the baseline period.
- Progestin opposed estrogen hormone therapy: These include prior use of E+P HT study drugs and subjects who used single-entity estrogen AND single-entity progestin medications during the baseline period (the two medications' usage does not need to overlap).
- Other opposed estrogen hormone therapy: These include prior use of estrogen-testosterone combination medications, conjugated estrogen-bazedoxifene, or the use of single-entity estrogen and single-entity testosterone medications during the baseline period (the two medications' usage does not need to overlap).
- No prior estrogen or progestin hormone therapy use (not including contraceptives). This will be a binary variable indicating no prior hormone therapy use.

Prior contraceptive use may be further divided into categories for time since last dispensing:

• <6 months;

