#### PFIZER CONFIDENTIAL

- 1-2 years;
- 2+ years.

The following variables will also be assessed using all available data during the baseline period, unless otherwise noted:

Demographic characteristics:

- Age, continuous, in years, on the date of the cohort-qualifying event;
- Region of residence in the US on the date of the cohort-qualifying date event. Categories of the region of residence will be as follows: Northeast, South, Midwest, or West. Region of residence will not be used as a covariate in Swedish analyses.
- Urbanicity (urban, suburban, rural)
- Calendar year of the index date.
- Duration of baseline period (in months).

Medical comorbidities (Annex 1: Appendix C and Appendix G):

- All-cause cancer (other than endometrial cancer and basal cell carcinoma);
- Breast cancer;
- Ovarian cancer;
- Thyroid cancer;
- Renal cancer;
- Colorectal cancer;
- Endometrial hyperplasia;
- Benign breast lumps (fibrocystic nodule);
- Polycystic ovary syndrome;
- Osteoporosis;
- Osteoarthritis;
- Vasomotor symptoms;

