#### PFIZER CONFIDENTIAL

- Unopposed progestin
- Progestin opposed estrogen hormone therapy
- Other opposed estrogen hormone therapy
- No prior hormone therapy

Prior use of these medications will be measured using the entire baseline period.

The following subgroup analyses will be conducted separately among the PS-matched cohorts of new users of LDVE, MDVE, and HDVC and non-users of vaginal estrogens to determine if the HR of endometrial cancer varies by the following covariates (Annex 1: Tables 3 and 6):

- Active ingredient at the cohort entry date:
  - Estradiol vaginal;
  - Conjugated estrogen vaginal.
- Formulation at the cohort entry date:
  - Vaginal cream;
  - o Vaginal ring;
  - Vaginal tablet;
  - Vaginal insert.
- Duration of use.
- Number of dispensings.
- Number of dispensings per formulation

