#### 9.9. Limitations of the Research Methods

#### 9.9.1. HIRD, US

The HIRD contains a dynamic population in which individuals may enter and exit as their insurance coverage changes over time. Because of this, assessment of vaginal estrogen use is limited to the period during which the individual is enrolled, and it is unknown whether individuals received vaginal estrogen prior to their enrollment. To address this concern, a study design that requires a minimum 12-month observation period prior to the start of follow-up is proposed. Individuals with vaginal estrogen use during this baseline interval will not be admitted to the study. Individuals who had a vaginal estrogen dispensing prior to enrollment may be inadvertently assigned to the non-user group. The effect of this potential exposure misclassification bias will be assessed in a sensitivity analysis restricted to patients with at least an 18-month baseline period.

In this study, diagnosis, procedure, and prescription codes will be used to reconstruct patients' medical histories. Certain risk factors for endometrial cancer such as ethnicity, BMI, pregnancy history, and lifestyle factors are not available in the HIRD or in Swedish registers. The impact of possible residual confounding will be assessed by conducting a quantitative bias analysis.

Possible outcome misclassification due to inaccurate coding of endometrial cancer will be addressed by validation of potential cases using medical records.

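### The 18-month baseline check (9.7.4, item 5) confounds look-back length with a change of population, and it leaves out the comparisons defined by no prior hormone therapy

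*Protocol*

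**What the plan says.** **Length of history in the main analysis.** Section 9.2.1 sets a floor: "HIRD: A minimum of 12 months of continuous eligibility in the HIRD prior to and including the study drug dispensing date". It then says how much history is used: "The baseline period includes all available enrollment data (HIRD) and medical history (HIRD, Sweden) on and prior to the index date". Section 9.3.4 describes prior hormone use and baseline covariates "using all available data prior to and including the index date", and demographics, comorbidities and medications "will also be assessed using all available data during the baseline period". For the prior-hormone-therapy subgroups, section 9.7.3.1 says: "Prior use of these medications will be measured using the entire baseline period". In section 9.3.4 only the utilization counts, pelvic radiation and the top-25 lists have a fixed 12-month window.

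**The check.** Item 5 of section 9.7.4 opens by saying that a longer, 18-month baseline will be considered. The analysis it specifies is the HR for LDVE versus non-users "among women who have a baseline period of at least 18 months of continuous HIRD enrollment". It names two aims. One is to see whether the 12-month and 18-month populations differ. The other is stated as: "Comparing results using different baseline durations will assess the effect of potential misclassification of covariates".

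**The limitation it answers.** Section 9.9.1 notes that women who used vaginal estrogen before enrolling could be placed among the non-users, and says that the effect of this exposure misclassification "will be assessed in a sensitivity analysis restricted to patients with at least an 18-month baseline period".

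**The concern.** A look-back check should change how much history is seen while leaving the women alone. Item 5 does nearly the opposite: it changes which women are analyzed, and for most of those who remain the history seen is the same as before. The result is then to be read as evidence on covariate misclassification (item 5) and exposure misclassification (section 9.9.1).

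In the HIRD, new-user status and absence of prior hormone therapy can rest on as little as 12 months of data. If the item 5 HR comes out close to the main HR, the report is likely to say that short look-back did not matter, and the design does not earn that conclusion. If the two HRs differ, the report cannot say why.

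Coverage is the second difficulty. Item 5 is run for LDVE versus non-users only. The secondary comparisons with E+P HT (section 9.7.3.2) and the no-prior-hormone-therapy stratum of primary objective 2 are defined by the absence of past use, so they too depend on look-back. Neither is checked.

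**Working it through.** **1. The plan's own figure.** Item 5 states no number, so the nearest is the HIRD study size in section 9.5.1. Inputs: HR 1.5, two-sided α 0.05 (two-sided is assumed, and it reproduces the figure), 80% power, 1:4 ratio, 74.5 events per 100,000 person-years, 2.4 years.

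- Events = (1.960 + 0.842)² / (0.2 × 0.8 × (ln 1.5)²) = 298.39, rounded up to 299. The plan has 60 + 239 = 299.
- LDVE users = 0.2 × 298.39 / 0.000745 / 2.4 = 33,377, as in the plan.
- Non-users = 0.8 × 298.39 / 0.000745 / 2.4 = 133,507. The plan has 133,504.

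**2. Is lost precision the weakness?** Expected events = retained LDVE users × 5 × 2.4 × 0.000745. Power = Φ(√(events × 0.16) × ln 1.5 − 1.96). The starting cohort is 152,941 LDVE new users (section 9.5.1). The retained shares are assumptions.

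| Retained | LDVE users | Events | Power at HR 1.5 |
|---|---|---|---|
| 75% | 114,706 | 1,025 | 99.9% |
| 50% | 76,471 | 684 | 98.9% |
| 25% | 38,235 | 342 | 85.1% |

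Precision is not the main weakness.

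**3. What changes for a retained woman?** Take a vaginal estrogen user with 30 months of enrollment before her index date.

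| Element | Main analysis | Item 5 |
|---|---|---|
| Prior vaginal estrogen, hysterectomy and cancer exclusions (9.2.2) | 30 months | 30 months |
| Prior hormone use, comorbidities, medications (9.3.4) | 30 months | 30 months |
| Utilization, pelvic radiation, top-25 lists (9.3.4) | 12 months | 12 months |

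Nothing changes. The difference between the two analyses comes from the women with 12 to under 18 months who leave.

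**4. How much misclassification does the restriction remove?** As an illustration (assumptions, not from the protocol), let enrollment beyond 12 months be exponential with mean m = 24 months, and let past use be missed with probability exp(−L/τ) at look-back L, with τ = 24 months.

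- Cohort average, main: exp(−12/24) × 24/(24 + 24) = 0.607 × 0.5 = 0.303.
- Cohort average, item 5: exp(−18/24) × 0.5 = 0.472 × 0.5 = 0.236.
- Share retained: exp(−6/24) = 78%.
- The retained women, in either analysis: 0.236. Change: zero.

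At m = 24, the fall in the cohort average is 0.123 to 0.074 for τ = 12 and 0.519 to 0.458 for τ = 48. Over m = 12 to 36, 61–85% are retained. The average falls because the shortest histories leave, not because anyone's history is read further back.

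Holding the women fixed does vary the history seen. Capping the same women at 12 versus 18 months moves the missed share from 0.607 to 0.472 (τ = 24), with 0.368 to 0.223 (τ = 12) and 0.779 to 0.687 (τ = 48).

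**5. Can the HR shift be interpreted?** Let the women who leave carry a share w of the information with HR 1.2, and the others have HR 1.5 (all assumed). Main log HR = (1 − w) ln 1.5 + w ln 1.2.

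| w | Main HR | Item 5 HR |
|---|---|---|
| 0.1 | 1.47 | 1.50 |
| 0.2 | 1.43 | 1.50 |
| 0.3 | 1.40 | 1.50 |

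The HR of 1.2 may come from missed history or from a real difference in short-enrolled women. The table is the same in both cases. It also treats the retained women as free of misclassification. Any misclassification they carry is present in both HRs, and the contrast does not show it.

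**The case against.** Several points on the other side stand.

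- **Some information remains.** A reader might infer that item 5 cannot measure misclassification at all. That goes too far: average missed history falls under the restriction (0.303 to 0.236 in the illustration), so a shift does carry information. What it cannot do is isolate the cause.
- **Population difference is a declared aim.** Item 5 says so, and as a population check it is legitimate. The fault lies in also reading it as a misclassification check.
- **Not every retained woman is certain to keep her look-back.** Section 9.2 allows non-users several qualifying visits, so an 18-month rule could move some to a later index date. The protocol does not say whether the propensity score is re-estimated and matching repeated, and that detail may be in the SAP. Either would add a further change to the contrast, not remove the confounding.
- **Item 5 is not the only safeguard.** Item 9 is a quantitative bias analysis of missed hysterectomy and missed prior estrogen or progestogen use, and Sweden is analyzed separately with at least 24 months of history. But item 9 is confined to LDVE and rests on plausible values with no stated data source, and the two countries differ in much more than look-back.
- **Scope.** LDVE versus non-users is the comparison the study is sized for, and it is one where the concern in section 9.9.1 applies. It would be tempting to say that the E+P HT comparisons depend most on look-back. The documents do not show a ranking, because LDVE versus non-users also relies on look-back through the rule of no prior vaginal estrogen. It is enough that the E+P HT comparisons depend on it and are unchecked. Items 2 and 6 already list all six comparisons, so wider coverage fits the protocol's own practice.

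**Conclusion.** The point holds as a design weakness in one sensitivity analysis. Because the main analysis already uses all available history, item 5 is a sample restriction that leaves the exclusions and covariates of retained vaginal estrogen users unchanged. It confounds look-back length with a change of population, so a shift is ambiguous and no shift is weak reassurance. It also leaves the E+P HT comparisons and the no-prior-hormone-therapy stratum without a look-back check, and item 9 does not fill that gap.

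This structural conclusion follows from sections 9.2.1, 9.2.2, 9.3.4, 9.7.3.1, 9.7.4 and 9.9.1 and needs no assumed number. The sizes (main HR 1.47–1.40 against 1.50; missed share 0.303 against 0.236) rest on assumed inputs and only illustrate the mechanism. They do not show that a large bias exists or would go undetected. The primary estimate is not in error. The change is worth making because section 9.9.1 relies on item 5 to answer a limitation the protocol itself names.

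**What to change.** 1. Keep item 5 as a check on whether longer-enrolled women give a different HR, and describe it that way in sections 9.7.4 and 9.9.1.
2. Add a contrast in the same women. Take women with longer enrollment (for example at least 18 or at least 36 months; the cut-off is a choice), fix the index date under the 12-month rule, and apply exclusions and covariates twice: once with history truncated to 12 months and once with all available history.
3. Report the share of women who look like new users, or appear to have no prior hormone therapy, on 12 months of history but have an earlier vaginal estrogen, hormone therapy or hysterectomy record.
4. Use that share as an empirical input to the item 9 bias analysis.
5. Include the E+P HT comparisons and, where counts allow, the no-prior-hormone-therapy stratum.

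The cost is protocol or SAP wording and re-runs on the same data source. Precision is lower, and the long-enrolled women are a selected subset, so the share may not carry over exactly to short-enrolled women. Both drawbacks are confined to a sensitivity analysis, and the primary analysis does not change.

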# NON-INTERVENTIONAL (NI) STUDY PROTOCOL

# **Study Information**

Title	A Comparative Observational Study Evaluating the Incidence Rate of Endometrial Cancer in Women aged 50 Years and Over Who Use Low-dose Vaginal Estrogen Unopposed by a Progestogen: A Post-authorization Safety Study in the United States and Sweden	
Protocol number	B2811020	
Protocol version identifier	Final Version (Original Protocol) 7.0	
Date	04 January 2022	
EU Post Authorization Study (PAS) register number	To be registered after protocol approval	
Active substances	1) Conjugated Estrogens Vaginal (Premarin)®	
	2) Estradiol Vaginal (Estring) ® ATC codes: G03CA03, G03CA57.	
Medicinal products	1) Premarin® Vaginal Cream (0.625 mg/gram).	
	2) Estring ® 2 mg (vaginal ring).	
Research question and objectives	Research Question: What is the incidence rate (IR) of endometrial cancer in postmenopausal women with a uterus who use low-dose vaginal estrogen (LDVE) unopposed by a progestogen compared to non-users and compared to users of estrogen- progestogen combination hormone therapy (E+P HT)?	
	Primary Objectives:	
	
 
To estimate and compare the IR of endometrial cancer in postmenopausal women aged >50 years, with a uterus, regardless of prior use of hormone therapy (defined as any estrogen, progestin, E+P HT use or other opposed estrogen hormone therapy), in the following groups:
 
	

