#### PFIZER CONFIDENTIAL

[figure not shown]
CT24-WI-GL02-RF023.0 Non-Interventional Study Protocol Template For Secondary Data Collection Study 20-May-2021

Page 20

The study population and characterization of the exposure and comparator groups are illustrated as a flowchart in Figure 2.

Due to the higher estrogen concentration for Premarin VC than non-Premarin LDVEs, higher daily doses of Premarin VC of >0.45 mg/day conjugated estrogen will be analyzed as a separate exposure group (HIRD only, as Premarin VC is not marketed in Sweden). This exposure group is referred to throughout as the HDVC group. Low-dose regimens  $\leq 0.3$  mg/day conjugated estrogen are also indicated for Premarin VC (i.e., 0.5 grams applied daily for 21 days or 0.5 grams applied twice weekly). These low-dose regimens will be evaluated as part of the LDVE exposure group.

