### 9.3.1. Exposures, Comparators, and Treatment Episodes

GPI codes will be used to identify vaginal estrogen and E+P HT products in the HIRD, (Annex 1: Appendix B) and ATC codes, formulation, brand name, and strength will be used to identify vaginal estrogen and E+P HT Swedish products (Annex 1: Appendix F). Gynecological visits for non-users will be identified in the HIRD using ICD-9-CM and ICD-10-CM diagnostic codes, HCPCS codes for annual exams, CPT codes for pap smear procedures, and physician's specialty code (Annex 1: Appendix C). Gynecological visits will be captured as non-primary outpatient care in the Swedish NPR. Proxies for gynecological visits (i.e., related procedure codes, specialist encounters, and/or reimbursement) will be considered, as appropriate.

Treatment episodes (Annex 1: Appendix I) will be created based on segments of continuous use among the study drug treatment groups, i.e., LDVE, MDVE, HDVC, and E+P HT. Continuous use is defined as consecutive drug dispensings for a treatment group, with no more than 90 days between the end of the days' supply of the earlier prescription and the dispensing date of the next prescription. In order to determine exposure status for vaginal estrogen users during the treatment episode, daily dose must first be computed for each prescription starting with the index dispensing. In the HIRD, daily dose for vaginal estrogen dispensings will be calculated as the drug strength dispensed multiplied by the drug quantity and divided by the days' supply. In Sweden, days' supply is not directly available from the SPDR. Thus, days' supply and daily dose will be estimated for each dispensed vaginal estrogen prescription based on assumptions such as defined daily dose and duration for use. For the E+P HT comparator group, dispensed amount of drug, drug strength and defined daily dose will be used to construct treatment episodes of continuous use. Exposure definitions will be further detailed in the statistical analysis plan (SAP).

The prescription daily doses of the vaginal estrogen dispensings will then be categorized as follows:

- LDVE: <10 mcg/day estradiol or <0.3 mg/day conjugated estrogen;
- MDVE: >10 25 mcg/day estradiol or >0.3 0.45 mg/day conjugated estrogen;
- HDVC: >0.45 mg/day conjugated estrogen.

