Vaginal estrogen users will enter the exposure group corresponding to the dose of their first study drug dispensing. Women whose first dispensing was E+P HT will enter the E+P HT comparator group. If a vaginal estrogen user changes dose categories or switches to E+P HT, she will be censored on the dispensing date of the new prescription. Similarly, if an E+P HT user switches to vaginal estrogen use, she will be censored on the vaginal estrogen dispensing date.

Patients may use different products and strengths for study drugs within their treatment group. If there are overlapping prescriptions for different products within the same treatment group, then it will be assumed that the patient stopped taking the first prescription drug and started the second prescription drug on the day it was dispensed (no stockpiling). If the patient has overlapping prescriptions for the same drug and dose, the prescriptions will be stockpiled, i.e., the overlapping days from the second prescription will be added to the end of the days' supply of the first

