#### PFIZER CONFIDENTIAL

Document reference number	Title					
Table 8: 8A and 8B	SENSITIVITY ANALYSES: Censoring criteria and the baseline period for the HIRD and Sweden					
Table 9: 9A and 9B	SENSITIVITY ANALYSIS: Incidence of endometrial cancer among vaginal estrogen users compared to non-users and E+P HT new users stratified by history of cancer for the HIRD and Sweden					
Table 10	SENSITIVITY ANALYSES: Incidence of endometrial cancer among HDVC new users compared to non-users and E+P HT new users stratified by number of dispensings of HDVC per year for the HIRD					
Table 11: 11A and 11B	SENSITIVITY ANALYSES: Incidence rates of endometrial cancer corrected for possible underascertainment of hysterectomy, prior estrogen use, and prio progestogen use among users of low-dose vaginal estrogen versus non-users for the HIRD and Sweden					
Table 12	POOLED ANALYSES: Incidence of endometrial cancer among users of LDVE and MDVE new users compared to non-users and E+P HT new users in the propensity-score matched cohorts in the HIRD, Sweden, and pooled					
Table 13	POOLED ANALYSES: Pooled incidence of endometrial cancer among vaginal estrogen users compared to non-users and E+P HT new users stratified by history of cancer in the HIRD and Sweden					
Appendix A	List of vaginal estrogen study drugs, HIRD					
Appendix B	Code list for treatment group study drugs, HIRD					
Appendix C	Code list for comorbidities and procedures, HIRD					
Appendix D	Code list for baseline medication use, HIRD					

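### Sensitivity analysis 7 looks for high cumulative exposure among HDVC users, but it stratifies by a count of dispensings that ignores the amount dispensed and is tied to no mg/day value

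*Protocol*

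**What the plan says.** Protocol 9.7.4, item 7 (HIRD only), is aimed at "patients who may have a cumulative exposure that is higher than the intended average daily dose". Under it, "the rate of endometrial cancer will be estimated among HDVC new users compared to non-users of vaginal estrogen", and also compared with E+P HT new users, by number of dispensings: "Number of dispensings will be categorized as ≤ 2 dispensings per year and >2 dispensings per year". The planned output, Table 10 in the Annex 1 list, is "stratified by number of dispensings of HDVC per year for the HIRD".

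Elsewhere the protocol expresses dose in mg/day. Section 9.1.2 states that "higher daily doses of Premarin VC of >0.45 mg/day conjugated estrogen will be analyzed as a separate exposure group". Section 9.3.1 sets the low category at up to 0.3 mg/day of conjugated estrogen and the moderate category at above 0.3 and up to 0.45 mg/day. Daily dose in the HIRD is "calculated as the drug strength dispensed multiplied by the drug quantity and divided by the days' supply", prescription by prescription. On early refills, 9.3.1 adds: "If the patient has overlapping prescriptions for the same drug and dose, the prescriptions will be stockpiled".

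Number of dispensings also appears as a stratifier for LDVE, MDVE and HDVC in primary objective 3 (Section 8) and in the subgroup analyses of 9.7.3.1. There it has no per-year cut-off and no stated cumulative-dose purpose.

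**The concern.** The aim is an amount per unit of time, while the measure is a number of pharmacy events. One dispensing of three tubes counts as one; three dispensings of one tube each count as three. No passage connects two dispensings per year with any mg/day figure, and item 7 does not say what the intended average daily dose is.

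What is at stake is whether Table 10 can be interpreted. If the upper stratum contains women with modest dispensed amounts and the lower stratum contains women with large ones, a flat or inverse pattern could reflect the stratifier and not the absence of a dose relation. The stockpiling rule adds to this. An early refill of the same drug and dose lengthens recorded use without raising recorded dose, so use above the recorded rate shows only in the total amount dispensed over time, which item 7 does not measure.

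**Working it through.** The protocol gives no derivation of the cut-off, so there is no figure to reproduce. The check is whether the cut-off corresponds to any of the protocol's dose limits.

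**Inputs from the protocol.** Cream strength 0.625 mg/g (Study Information). Category limits 0.3 and 0.45 mg/day (9.1.2, 9.3.1). Cut-off at 2 dispensings per year (9.7.4, item 7).

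**Assumed inputs.** Grams per dispensing, 14 to 90 g. Days' supply per dispensing, 30 to 90 days.

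**1. Yearly amount at each limit** = limit × 365 / 0.625.
- 0.3 mg/day: 109.5 mg / 0.625 = 175.2 g per year.
- 0.45 mg/day: 164.25 mg / 0.625 = 262.8 g per year.

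**2. Grams per dispensing needed to reach the limit.**
- Two per year: 175.2 / 2 = 87.6 g for 0.3 mg/day; 262.8 / 2 = 131.4 g for 0.45 mg/day.
- Three per year (the lowest whole count above the cut-off): 175.2 / 3 = 58.4 g; 262.8 / 3 = 87.6 g.

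**3. Average over a year** = dispensings × grams × 0.625 / 365, in mg/day.

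| Grams per dispensing | 2 per year | 3 per year |
|---|---|---|
| 14 | 0.048 | 0.072 |
| 30 | 0.103 | 0.154 |
| 60 | 0.205 | 0.308 |
| 90 | 0.308 | 0.462 |

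Below 58.4 g, both two and three dispensings per year lie within 0.3 mg/day. At 30 g, four and five dispensings give 0.205 and 0.257 mg/day, also in the upper stratum and also in the low-dose range. It takes 175.2 / 30 = 5.84 dispensings to reach 0.3 mg/day and 262.8 / 30 = 8.76 to reach 0.45. At 90 g, two dispensings already pass 0.3 and three pass 0.45.

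**4. Ordering.** Take two women, both HDVC by the per-prescription rule:
- Two 90-day supplies at 0.6 mg/day: 2 × 90 × 0.6 = 108 mg, lower stratum.
- Three 30-day supplies at 0.46 mg/day: 3 × 30 × 0.46 = 41.4 mg, upper stratum.

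The count ranks them in the wrong order. This does not need a common quantity per dispensing, only that days' supply can differ between women.

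**5. A possible origin of the cut-off.** The 0.5 g twice-weekly regimen named in 9.1.2 uses 0.5 × (2/7) × 365 = 52.1 g per year, or 52.1 / 30 = 1.74 dispensings of 30 g. The other low-dose regimen named there, 0.5 g daily for 21 days (28-day cycle assumed), uses 0.5 × 0.75 × 365 = 136.9 g, or 4.56 dispensings. At 30 g, a cut-off of two falls between two low-dose regimens.

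**The case against.** The strongest reply has several parts.

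- **Quantity is unknown.** Grams per dispensing appear nowhere in the protocol, and from 58.4 g upward the third dispensing does reach 0.3 mg/day. This stands. A reader might infer that the upper stratum never identifies women above the intended dose, or that the analysis cannot serve its purpose. The documents do not support that: it depends on the quantity.
- **The yardstick differs.** The protocol's limits apply to each prescription over its days' supply. Every HDVC woman exceeds 0.45 mg/day on that scale at index and is censored if her category changes. This stands too, so a low yearly average does not mean she was misclassified. But item 7 itself speaks of cumulative exposure and counts per year, and follow-up continues through gaps between treatment episodes (9.3.1). An average over elapsed time is therefore a fair scale for this item.
- **The item claims little.** It concerns women who may have higher exposure, and for one product at one strength refill frequency is a coarse proxy. Step 5 gives a plausible reason for the cut-off. That reason is unstated, and it would still place the cut-off within the low-dose range.
- **LDVE and MDVE are not ignored.** A reader might infer that no analysis examines frequent refillers in those groups. Objective 3 and 9.7.3.1 do stratify them by number of dispensings, though with the same limitation and no cumulative-dose aim. Nor does stockpiling mean that such a woman can never change category. Dose is computed for each prescription, so a refill with a shorter recorded days' supply can move her and censor her.
- **The SAP may refine exposure definitions.** True, but the protocol already fixes the measure, the cut-off and the group for this item.

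**Conclusion.** The point holds in a limited form. Item 7's stratifier does not measure what the item sets out to measure, its cut-off is tied to no dose, and the dose it refers to is undefined. Whether women in the upper stratum average within the low-dose range depends on the unstated quantity per dispensing. It is so for three dispensings per year below 58.4 g each, and not so above that. The misordering in step 4 can arise whenever days' supply varies between women. The likely consequence is mixed strata and a blurred gradient.

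The effect is confined to one HIRD sensitivity analysis. It does not reach the primary LDVE comparison, and nothing here suggests that the main hazard ratios are biased. It is an inexpensive improvement.

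**What to change.** In 9.7.4 item 7 and Table 10:

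1. State what the intended average daily dose means.
2. Replace the count with cumulative dispensed conjugated estrogen (strength × quantity, summed to date) divided by time since the index dispensing. Update it over follow-up using past dispensings only, and evaluate it from the end of the six-month induction period.
3. Do not restart the denominator at later episodes. A restart would inflate the ratio early: one 30 g dispensing is 18.75 mg, which stays above 0.45 mg/day for 18.75 / 0.45 ≈ 41.7 days whatever the actual use.
4. Use the protocol's existing category limits (0.3 and 0.45 mg/day) as cut points, labelled as average dispensed amount so that they are not confused with the per-prescription dose category.
5. Keep the number of dispensings as a descriptive row.
6. Where case counts allow, run the same tabulation for Premarin cream users in LDVE and MDVE.

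Strength and quantity are already needed for the daily-dose formula in 9.3.1, so no new data are required. The cost is some programming, additional table rows and small cells in the upper stratum.
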